#### 5.2.1 **Procedures for randomisation**

Randomisation codes will be assigned strictly sequentially as patients become eligible for randomisation. An eligible patient will be randomised to the lowest available randomisation code at the centre.

Randomisation codes will be computer generated by AstraZeneca R&D using the AstraZeneca Global Randomisation System (GRand). There will be no formal stratification.

# 5.3 Procedures for handling patients incorrectly enrolled or randomised

**Patients who fail to meet the inclusion/exclusion criteria** should not, under any circumstances, be enrolled or randomised. There can be no exceptions to this rule.

Where patients that do not meet the selection criteria are randomised in error or incorrectly started on treatment, or where patients subsequently fail to meet the study criteria post initiation, a discussion should occur between the AstraZeneca Study Delivery Team Physician and the Investigator regarding whether to continue or discontinue the patient from treatment.

The AstraZeneca Study Delivery Team Physician is to ensure all such decisions are appropriately documented. In situations where an agreement cannot be reached, the patient should have their study therapy stopped.

# 5.4 Blinding and procedures for unblinding the study

## 5.4.1 Methods for ensuring blinding

AZD9668 30mg will be provided as tablets for oral administration and with matching placebo tablets of the same appearance. Patients in both treatment arms will take the same dosage of investigational product ie, 2 tablets twice daily.

## 5.4.2 Methods for unblinding the study

Individual treatment codes, indicating the treatment randomisation for each randomised patient, will be available to the investigator(s) or pharmacists at the study centre. All code break envelopes must be kept in a safe but accessible place.

The treatment code should not be broken except in medical emergencies when the appropriate management of the patient requires immediate knowledge of the treatment randomisation. The investigator documents and reports the action to AstraZeneca, without revealing which study treatment the patient received to AstraZeneca staff.

A patient whose randomisation code has been broken will be discontinued from the study (see Section 5.8).

AstraZeneca retains the right to break the code for SAEs that are unexpected and are suspected to be causally related to an investigational product and that potentially require expedited reporting to regulatory authorities. Treatment codes will not be broken for the planned analyses of data until all decisions on the evaluability of the data from each individual patient have been made and documented.

On completion of the study, the monitor will ensure and document the return of the code envelopes and also document the reason for any opened envelope, dated and signed by the principal investigator.

# 5.5 Treatment(s)

#### 5.5.1 Identity of investigational product

Investigational product	Dosage form and strength	Manufacturer
AZD9668	Coated tablet 30 mg (corresponding to 39.5 mg AZD9668 tosylate)	AstraZeneca
Placebo to AZD9668	Coated tablet placebo	AstraZeneca

The formulation number and batch number will be recorded in the Study Master File and identified in the Clinical Study Report.

Tablets will be supplied at Visits 2, 4 and 5 in a box containing 2 bottles with 72 tablets each. This is sufficient for 28 days+/-3 days dosing twice daily plus overage.

#### 5.5.2 Identity of additional study drugs

	Salbutamol sulphate, used as reliever medication during run-in and treatment period	Tiotropium bromide, used for maintenance treatment during run-in and treatment period
Trade Name:	See Section 5.5.3.2	Spiriva® given via HandiHaler®
Active ingredients:	salbutamol sulphate	tiotropium bromide
Excipients:	dependent on product provided	lactose monohydrate
Dosage form:	pMDI	inhalation powder, hard capsules
No. of doses:	200 actuations	30 capsules/package
Strength:	100 μg/dose	18 μg/dose
Manufacturer:	dependent on product provided	Boehringer Ingelheim

#### 5.5.3 Doses and treatment regimens

#### 5.5.3.1 Randomised treatment during treatment period

At Visit 2 patients will receive either AZD9668 tablets 30 mg or placebo tablets for oral use. Patients will take 2 tablets twice daily for 12 weeks, with doses approximately 12 hours apart. The patients will be issued with sufficient tablets to allow self-dosing until Visit 4.

At Visit 4 the patients will be issued with sufficient tablets to allow self-dosing until Visit 5.
At Visit 5 the patients will be issued with sufficient tablets to allow self-dosing until Visit 6.

The first dose of investigational product will be the morning dose taken in the clinic at Visit 2 after completing post-bronchodilator spirometry measurements. The last dose of investigational product will be the morning dose taken in the clinic at Visit 6. In the morning of Visit 3 to 6 the investigational product must not be taken at home. Instead it will be taken at the clinic after completing post-bronchodilator spirometry and other pre-dose clinical assessments. All other doses will be taken by the patient at home.

It is not necessary for the patients to restrict food around administration of their doses. All doses will be taken with water.

## 5.5.3.2 Open treatment during enrolment, run-in and treatment periods

Patients who use inhaled glucocorticosteroids (GCS) (including combination therapy with long-acting  $\beta_2$ -agonists (LABA) before the study should, based on the investigator's judgement that it is safe for the patient and after signing informed consent, stop inhaled GCS (including combination products) at Visit 1a, >3 weeks before attending the screening visit (Visit 1b), i.e., these patients will be on tiotropium for at least 5 weeks before randomisation. These patients will receive tiotropium at the same occasion (Visit 1a).

Patients not taking inhaled GCS prior to the study will begin treatment with tiotropium at Visit 1b. For these patients, Visit 1a can be performed closer to Visit 1b. The informed consent must be signed prior to any medications being withheld and timeframes for withholding medications taken into account (see Section 5.6.3). At Visit 1b, all patients must be on tiotropium alone as maintenance therapy.

Eligible patients will be enrolled to a 2 week run-in period, during which all patients will be treated with tiotropium 18 µg once daily.

The patients will be provided with maintenance and reliever medication throughout the run-in period and treatment period. Spiriva® (tiotropium bromide, 18 µg/dose, 30 capsules/package) will be provided by AstraZeneca R&D or be supplied locally by the AstraZeneca Marketing Company (MC). The reliever medication, VentolinTM EvohalerTM (salbutamol sulphate 100 µg/dose, 200 actuations), will be supplied locally by the AstraZeneca MC or prescribed by the investigator. Products provided must contain the same active ingredient and use the same dosage form and be an equivalent strength as the medications specified in Section 5.5.2. When tiotropium and salbutamol are locally sourced local regulatory guidelines will be adhered to.

If the patient prefers to use their existing reliever medication (SABA only, dry powder inhalers are allowed) they may do so. If so, the same SABA should be used throughout the study.

When receiving the reliever and maintenance medications, the patient will be carefully instructed and trained on how to inhale from the inhalers to ensure good inhalation technique during the study. Written information will be provided to each patient in his/her local language.

Maintenance and reliever medication will be first dispensed at either Visit 1a or Visit 1b, depending on which COPD treatment patients use prior to the study. Maintenance and reliever medication will then be dispensed when needed at Visits 2 to 5. After Visit 6, the patients will return to their ordinary COPD treatment, at the discretion of the investigator.

**Maintenance medication:** Tiotropium 18  $\mu$ g/dose will be given via HandiHaler® inhaler in an open manner, 1 oral inhalation every morning throughout the study. For patients on inhaled GCS (including combination therapy with LABA), Visit 1a should be > 3 weeks before Visit 1b to allow 3 weeks withdrawal of inhaled GCS and treatment with tiotropium before the run-in period. At Visit 1b all patients must be on tiotropium alone as maintenance therapy.

On visit days the maintenance medication will be taken at the clinic after completing spirometry (post bronchodilator) and other pre-dose clinical assessments.

**Reliever medication:** Salbutamol sulphate 100  $\mu$ g/dose will be provided as reliever medication. The reliever medication provided by AstraZeneca should be used by the patient during the study period from Visit 1a/1b to Visit 6. If the patient chooses to use his/hers existing SABA as reliever medication during the study, the salbutamol inhaler provided by AstraZeneca should be used for all post-bronchodilator measurements at the clinic. Patients will be asked to refrain, if possible, from taking the reliever medication at least 6 hours prior to the clinic visits.

## 5.5.4 Labelling

The packaging and labelling of centrally provided study drugs will be performed by Investigational Products (IPS) AstraZeneca R&D or their designee. All supplies and labels will be prepared in accordance with Good Manufacturing Practice (GMP) and local regulatory guidelines. The labels will fulfil GMP Annex 13 requirements for labelling. Label text will be translated into local language.

The labels will include the following information:

- Name and address of sponsor
- Study drug dosage form, route of administration and quantity of dosage units
- Storage conditions

- Packaging Lot ID
- Study code
- Enrolment code and/or randomisation code
- Directions for use
- Expiry date
- Visit number (if applicable)
- The following standard statements
  - "for clinical trial use only" or similar wording
  - "keep out of the reach of children".

The bottles will be labelled with a single panel label. The boxes, containing 2 bottles, will be labelled with a 2-panel label. One part of the label will be permanently affixed to the box and the other part will be a tear-off part to attach to the drug accountability form in the Investigator's Study File (ISF) at the time of administration.

### 5.5.5 Storage

All study drugs should be kept in a secure place under appropriate storage conditions. The investigational product label on the bottle and boxes specifies the appropriate storage.

# 5.6 **Concomitant and post-study treatment(s)**

### 5.6.1 Medications allowed during the study

Medication allowed from Visit 1b:

- tiotropium alone as maintenance therapy. Patients should not take the morning dose at home on visit days.
- salbutamol (albuterol) sulphate or patient's own SABA as reliever medication. Patients will be asked to refrain from taking reliever medication at least 6 hours prior to clinic visits.
- other medication, which is considered necessary for the patient's safety and well being, may be given at the discretion of the investigator.

All medication, including study drugs, should be recorded in the appropriate sections of the electronic Case Report Form (eCRF).

#### 5.6.2 Medications allowed for the treatment of exacerbations

Medication allowed from Visit 2 and throughout the study:

- Oral steroids, ie, prednisolone/prednisone
- Antibiotics when signs of infection are present
- Parenteral steroids (single injections but not depot formulations)
- All disallowed medications listed in Section 5.6.3 are allowed during emergency room treatment/hospitalization due to an exacerbation (except depot parenteral corticosteroids and non-cardioselective β-blockers).

#### 5.6.3 Disallowed medications

#### 5.6.3.1 Treatments to be withdrawn before/at Visit 1b until Visit 6

	Time limits prior to Visit 1b	
Inhaled SABA (allowed throughout the study but withheld 6 hours prior to Visit 1b and Visits 2-6 if possible)	6 hours	
Inhaled LABA	48 hours	
Combinations of inhaled GCS/LABA	at Visit 1a, >3 weeks prior to Visit 1b	
Oral β 2 -agonists as follows: - short acting formulations - depot formulations - long acting formulations	8 hours 24 hours 48 hours	
Transdermal β 2 -agonists	24 hours	
Parenteral β 2 -agonists	48 hours	
Inhaled short-acting anticholinergics	8 hours	
Inhaled long-acting anticholinergics (except for tiotropium study drug which is allowed throughout the study but withheld 24 hours prior to clinic visits if possible)	24 hours	
Xanthine-containing derivatives once daily	48 hours	
Xanthine-containing derivatives twice daily	24 hours	
Any medication containing ephedrine	24 hours	

	Time limits prior to Visit 1b
Inhaled GCS	3 weeks
Oral, parenteral and rectal GCS	4 weeks
Depot parenteral GCS	12 weeks
Disodium cromoglycates, antihistamines and mucolytics (eg, N-acetylcystein)	At Visit 1b
Leukotriene antagonists and 5-Lipoxygenase (5-LO) inhibitors	48 hours

In addition, treatment with non-cardioselective  $\beta$ -blockers (including eye-drops) is prohibited from Visit 1b and throughout the study.

### 5.6.3.2 Treatments to be withdrawn before/at Visit 2 until Visit 6

	Time limits prior to Visit 2
Immunomodulatory agents	8 weeks

 
The following CYP2C9 substrates:
 
Phenytoin
 
Warfarin, coumarins
 
Fluvastatin
 
High dose, continuous Non-Steroidal Anti-Inflammatory
 
Drugs (NSAIDs) (documented prn use of NSAIDs is allowed)
 
	At Visit 2 At Visit 2 At Visit 2 At Visit 2

The last dose of study drug (tiotropium and investigational product) will be given at Visit 6. Patients will then return to their ordinary COPD treatment at the discretion of the investigator.

## 5.7 Treatment compliance

The administration of all medication (including investigational products) must be recorded in the appropriate sections of the eCRF and the drug accountability/dispensing record. Investigational product accountability will be performed at Visits 4, 5 and 6. Intake of investigational product will be recorded in the eDiary morning and evening as "yes" or "no". Intake of maintenance medication will be recorded in the morning eDiary as "yes" or "no". This does not mean that the patient has an option not to take the study medications but will be used as a measures of compliance.

### 5.7.1 Accountability

The study drug provided for this study will be used only as directed in the study protocol.

The study personnel will account for all study drugs dispensed to and returned from the patient.

The AstraZeneca monitor will ensure that all drug handling procedures are followed correctly. The destruction of used and unused study drug should preferably be done by the study site. If destruction at the study site is not possible, the monitor should return the study drug to the organisation responsible for distribution (for example the distribution site) and will account for all received study drugs and return all unused study drugs. All destruction of study drug must be done by an appropriately qualified organisation.

AstraZeneca personnel will account for all study drugs received at the site, unused study drugs and for appropriate destruction. Certificates of delivery, destruction and return should be signed.

# 5.8 Discontinuation of a patient from the study

Patients may be discontinued from the study in the following situations:

- 1. Patient decision. The patient is at any time free to discontinue treatment, without prejudice to further treatment
- 2. Severe non-compliance to study protocol as judged by the investigator and/or AstraZeneca
- 3. Risk to patients as judged by the investigator and/or AstraZeneca
- 4. Incorrectly enrolled patients
- 5. Patient lost to follow-up
- 6. Pregnancy
- 7. Treatment code prematurely broken by the investigator

Development of any of the specific discontinuation criteria listed below:

- 8. Change in QTcB >60 msec from baseline value (pre-dose Visit 2) or QTcB >500 msec, (to be confirmed by repeat ECG performed within 30-60 minutes of the initial assessment), or any other clinically significant ECG abnormality.
- 9. An ALT / AST level ≥ 3x upper limit of normal (ULN) (confirmed on repeat sample) or any pattern of liver function test (LFT) abnormalities that the investigator or AstraZeneca consider indicates an unacceptable level of risk to the patient. These events should be followed up as appropriate for the patient. A

guidance document for the follow-up of liver function parameters of concern is provided separately.

- 10. Evidence of haemolysis as evidenced by the following:
  - Reticulocyte count of over 5%, **AND** at least 2 of the following:
    - a drop in haemoglobin below 10.5 g/dL
    - decrease of 25% in haptoglobin. (The value post-dose to be compared with the average of 2 pre-dose values. The value should also be 15% below lower limit of normal (LLN)
    - increase of 25% in unconjugated bilirubin or lactate dehydrogenase (LDH). (The value post-dose to be compared with the average of 2 pre-dose values. The value should also be 15% above upper limit of normal (ULN).
- 11. A platelet count of below  $80 \ge 10^9$ /L confirmed by a repeat test (in the absence of obvious platelet clumping in a peripheral blood film).

Specific reasons for discontinuing a patient from the genetic research are detailed in Appendix D.

Withdrawal of consent for donated biological samples is included in Section 7.5.

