patients treated with AZD9668) have been completed, and a Phase IIa study in patients with cystic fibrosis is ongoing. AZD9668 was generally well tolerated in these studies. One patient in the bronchiectasis study had raised transaminases during treatment with AZD9668 however there were no associated changes in bilirubin or other liver function tests. A relationship to study drug for this patient could not be excluded. This or a similar pattern of liver function changes, has not been seen in any other patients or healthy volunteers treated with AZD9668. To minimise any possible risk of liver effects to patients, patients with an alanine aminotransferase (ALT)/aspartate aminotransferase (AST) level  $\geq 1.5$  x upper limit of normal (ULN) will be excluded from the study. Study drug will be discontinued if patients have an ALT/AST level  $\geq 3$  x upper limit of normal, or if patients develop any pattern of liver function test abnormality that the Investigator or AstraZeneca considers as indicating an unacceptable level of risk to the patient. A guidance document has been created for the follow up of both liver function parameters that reach the discontinuation criteria, and also those that have not reached the discontinuation criteria but are of concern, see Section 5.8.

To mitigate the other risks that may be associated with the pre-clinical signals summarised in Section 1.1, in addition to standard inclusion/exclusion criteria, subjects with an estimated creatinine clearance of <50 mL/min will be excluded from the study (see Section 4.3). Haematological and biochemical parameters including evidence for haemolysis will be monitored during the study. Although no significant QT abnormalities were observed in clinical studies to date, patients with a prolonged QTc value will not be enrolled. A 12 lead ECG will be recorded at screening, prior to the first dose of AZD9668 at the randomisation visit and around 4 hours post-dose at this visit and at regular intervals during the study thereafter. Patients will be withdrawn if they develop QTc > 500 msec or a prolongation of QTc > 60 msec compared to baseline.

Additionally, an Independent Safety Review Committee (SRC) will review the safety data on an ongoing basis, throughout the study (see Section 12.4 for further details).

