# (Continued)

Table 1	Visit schedule	(Continued)
Visit No.	Type of Visit	No. of weeks ± no of days between visits
5	Treatment visit	8 weeks $\pm 3$ days after Visit 2
6	End of treatment visit	12 weeks -3 days after Visit 2
7	Follow-up Visit	14 weeks ±3 days after Visit 2

Study Visit	Visit 1a	Visit 1b	Visit 2	Visit 3	Visit 4	Visit 5	Visit 6	Visit 7
Written informed consent	х							
Demography (date of birth, sex and race)	X							
Physical examination		х	Х	Х	Х	х	Х	Х
Height/Weight		X					x (weight only)	
Medical/surgical history		х						
COPD history		X						
Smoking history		X						
Smoking habits			Х				X	
MSCT (pre-visit, see Section 6.3.1)			2 to 7 days before Visit 2				0 to 3 days before Visit 6	
Clinical chemistry, haematology and urinalysis b		X	Х	Х	х	X	X	Х
Pregnancy test a		х	Х					х
Inclusion/exclusion criteria	х	х	Х					
Randomisation			х					
Vital signs, 12-lead ECG b		х	x c	Х	Х	х	х	х
Spirometry (FEV 1 , FVC, SVC) b		Х	Х	Х	Х	Х	Х	
Body Plethysmography (IC, TLC, FRC, RV, SGaw) b			X				X	
DL CO b			Х				Х	
Dispense maintenance and reliever drugs	(x)	X	(x)	(x)	(x)	(x)		

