#### Table 2Study Plan

### (Continued)

Table 2

Study Visit	Visit 1a	Visit 1b	Visit 2	Visit 3	Visit 4	Visit 5	Visit 6	Visit 7
Administer AZD9668 morning dose at clinic after spirometry			Х	х	x	х	х	
AZD9668/placebo Dispense/ Check/ Return (d/c/r)			d		d / c / r	d / c / r	c / r	
e-PRO / Home spirometry device d training/ dispense/ check/ return (t / d / c / r)	(t)	t / d	С	С	с	С	c / r	
BCSS, EXACT, FEV 1 , PEF and intake of study drugs - assessed at the patient's home		x					X	
SGRQ-C b		(x) e	Х				Х	
Desmosine urine sampling			Х		Х		Х	
Concomitant medications recorded	Х	Х	Х	Х	Х	Х	Х	Х
Adverse events		Х	Х	Х	х	х	х	Х
Exacerbation recording		X	Х	Х	X	Х	Х	X
Pharmacogenetics blood sampling (optional) f			Х					

a Pregnancy tests at Visit 1b and 7 to be taken in blood and pregnancy test at Visit 2 to be taken in urine.

b Assessments to be done pre-dose of AZD9668 at Visits 2-6.

c A second ECG and vital signs measurement should be done 3-4 hours post-dose of AZD9668 at Visit 2.

d ePRO including BCSS and EXACT questionnaires, Questions on intake of study drugs and Spirometry measurements of PEF and FEV1,

e Training session, data not to be collected in study database.

f Only 1 pharmacogenetic sample is required. This should be taken at Visit 2 or any subsequent visit once separate written informed consent has been obtained.

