### 6.4.5 Laboratory safety assessment

Blood and urine samples for determination of clinical chemistry, haematology, and urinalysis will be taken at the visits indicated in the Study Plan (see Table 2) and before intake of the morning dose of investigational product. Blood samples will be analysed at a central laboratory. Urinalysis will be performed locally at the study site using dipsticks provided by the central laboratory.

The central laboratory will provide all the materials required for blood and urine sampling. Instructions for labelling, storage and shipping will be detailed in the laboratory manual. The central laboratory will also provide up to date reference ranges throughout the study for the management of patient safety.

Clinically relevant deviations from the reference range in the lab values will be handled as outlined in Section 6.4.3, adverse events based on examinations and tests.

The following laboratory variables will be measured:

Haematology		
Haemoglobin	Mean Cell Volume (MCV)	Platelet count
Erythrocyte count	Mean Cell Haemoglobin (MCH)	Reticulocyte count
Haematocrit	Mean Cell Haemoglobin Concentration (MCHC)	Leucocyte count (absolute and percentage including neutrophil, lymphocyte, monocyte, eosinophil and basophil counts)

Clinical Chemistry			
Creatinine	Potassium	Creatinine kinase (CK) a	
C-Reactive Protein (CRP)	Calcium, total Lactate dehydroger		
Total bilirubin b	Sodium Glucose		
Alkaline phosphatase	Cholesterol	Free thyroxine (T4) (Visit 1b only)	
Aspartate aminotransferase (AST)	Triglycerides	Thyroid stimulating hormone (TSH) (Visit 1b only)	
Alanine aminotransferase (ALT)	Urea	Haptoglobin	
Albumin	Gamma Glutamyltransferase (GGT)	hCG c	

a CKMB fraction to be measured if CK is elevated >2 x ULN (as detailed in the laboratory manual)

b Unconjugated and conjugated bilirubin will be measured if the total bilirubin is elevated

c Visit 1b and Visit 7, only for female patients

For blood volumes see Section 7.1.

Urinalysis		
Protein	Glucose	Haemoglobin

Please refer to Section 5.8 for the discontinuation criteria relating to laboratory safety variables.

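### The haemolysis discontinuation criterion compares unconjugated bilirubin with two pre-dose values that the laboratory plan does not collect when total bilirubin is normal; the reach is limited

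*Protocol*

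**What the plan says.** Section 5.8 of the protocol, criterion 10, defines haemolysis as a reticulocyte count over 5% together with "at least 2 of the following": haemoglobin below 10.5 g/dL; a fall in haptoglobin; and, as third sub-item, an "increase of 25% in unconjugated bilirubin or lactate dehydrogenase (LDH). (The value post-dose to be compared with the average of 2 pre-dose values". A further condition on the third sub-item follows: "The value should also be 15% above upper limit of normal (ULN".

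Table 2 (Study Plan) schedules "Clinical chemistry, haematology and urinalysis" at Visit 1b and at Visits 2 to 7, with the footnote "Assessments to be done pre-dose of AZD9668 at Visits 2-6". The planned pre-dose chemistry samples are therefore Visit 1b and Visit 2.

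Section 6.4.5 lists total bilirubin in the chemistry panel and adds in footnote b: "Unconjugated and conjugated bilirubin will be measured if the total bilirubin is elevated". The same section sends the reader to Section 5.8 for the laboratory discontinuation criteria. It provides no other baseline measurement of the fraction.

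On a separate matter, Section 1.4 says of the liver criterion: "Study drug will be discontinued if patients have an ALT/AST level" reaches 3 x ULN, and it words the QTc criterion as equally firm. Section 5.8 places both under the lead-in "Patients may be discontinued from the study in the following situations".

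**The concern.** A stopping rule can be applied only if the data it names are collected. Here the protocol itself fixes both the rule and the test schedule, and they do not match, so this is not a detail left to an analysis plan. Increased red-cell turnover is one of the preclinical signals in Section 1.1, and Section 1.4 offers monitoring for haemolysis as part of the risk mitigation. Section 5.8.1 has criteria 8 to 11 recorded as a reason for termination in their own right. A site that sees bilirubin rise after dosing in a patient whose total bilirubin was normal before dosing has no stated way to decide whether the bilirubin half of the sub-item is met.

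**Working it through.** The criterion rests on no sample size or power figure, so there is no plan figure to reproduce. The check compares what the rule needs with what is collected, then asks when the gap could change a decision.

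**1. Data needed and data collected**

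| Analyte in criterion 10 | Needs two pre-dose values | Collection under Section 6.4.5 and Table 2 |
|---|---|---|
| Reticulocytes | No, fixed threshold | Visits 1b to 7 |
| Haemoglobin | No, fixed threshold | Visits 1b to 7 |
| Haptoglobin | Yes | Visits 1b to 7 |
| LDH | Yes | Visits 1b to 7 |
| Unconjugated bilirubin | Yes | Only when total bilirubin is elevated |

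The three footnotes to the chemistry panel concern CK, bilirubin and hCG, so no condition attaches to LDH or haptoglobin. Only the last row fails. A normal total at one of the two pre-dose visits is enough, because the rule asks for the average of two values.

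**2. What the ULN condition settles**

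Let B be the average pre-dose value and P the post-dose value, both in multiples of the ULN for unconjugated bilirubin. The sub-item needs P ≥ 1.25 × B and P ≥ 1.15.

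- If B ≤ 1.15 / 1.25 = 0.92, the second condition implies the first, and the missing baseline does not affect the answer.
- If B lies between 0.92 and 1.00, the rise needs P of at least 1.25 × B, which is between 1.15 and 1.25. The answer is open only for P in that band. Example: with B = 0.96 the rise needs P ≥ 1.25 × 0.96 = 1.20, so P = 1.17 passes the ULN condition but not the rise.

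The second bullet assumes that the unmeasured fraction was within its own normal range. The protocol gives no ULN for it, and a normal total does not strictly guarantee this.

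**3. What is lost if bilirubin is never counted**

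Given reticulocytes over 5%, score haemoglobin (H), haptoglobin (G), unconjugated bilirubin (U) and LDH (L) as met (1) or not met (0). This gives 2^4 = 16 patterns. The rule triggers when H + G + max(U, L) ≥ 2.

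- As written: H and G both met, 4 patterns; exactly one of them met and U or L met, 2 × 3 = 6. Total 10.
- Without U: H and G both met, 4 patterns; exactly one of them met and L met, 2 × 2 = 4. Total 8.

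The 2 lost patterns have bilirubin met, LDH not met, and exactly one of haemoglobin and haptoglobin met. These are counts of patterns, not probabilities.

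**4. How many patients would have both pre-dose values**

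The protocol gives no share of patients with elevated total bilirubin. For an assumed share p of 2.5% to 20% per visit among about 50 patients:

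- the same patients elevated at both visits: 50p = 1.25 to 10;
- the two visits independent: 50p² = 0.03 to 2.

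On that assumption most patients would lack the baseline. By steps 2 and 3, this does not mean that the rule fails in most patients.

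**The case against.** The strongest reply is that the gap rarely changes a decision. The ULN condition settles the 25% rise over most of the normal range, LDH is an alternative within the same sub-item, and haemoglobin plus haptoglobin satisfy the rule without the third sub-item. Criterion 3 allows discontinuation for risk judged by the investigator or sponsor, criterion 9 covers any worrying liver-test pattern, and the Safety Review Committee (Section 12.4) reviews safety data throughout. All of this stands and limits the finding. It does not remove the contradiction: the protocol does not tell sites to infer the rise from the ULN condition, and a baseline above 0.92 x ULN leaves the question open.

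A reader might infer that the haemolysis rule, or its whole third sub-item, cannot be applied in nearly all patients. The documents do not support this: only the bilirubin half lacks its input, and the protocol gives no bilirubin distribution. A reader might also infer that the comparison of safety discontinuations between arms is compromised. Sections 11.2 and 12.2 plan descriptive safety summaries with no between-arm test of such discontinuations, blood is analysed at one central laboratory, and nothing shows that sites would apply the rule differently by arm.

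On the wording in Section 1.4, it can fairly be said that the lead-in in Section 5.8 is a general one that also covers patient decision and loss to follow-up. That makes the mismatch minor, but it still leaves open whether the liver and QTc criteria are mandatory.

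**Conclusion.** The inconsistency is real and narrow. Where total bilirubin is normal at Visit 1b or Visit 2, the unconjugated-bilirubin half of the third sub-item of criterion 10 cannot be calculated as written. In practice the missing value matters only when all of these hold: reticulocytes exceed 5%, exactly one of haemoglobin and haptoglobin is met, LDH is not met, and the post-dose fraction passes the ULN condition from an unmeasured baseline above about 0.92 x ULN. If sites instead treat an uncalculable bilirubin as not met, 2 of the 10 triggering patterns are lost. The 0.92 figure is exact arithmetic. The upper end of the open range assumes that the baseline fraction did not exceed its own ULN, which the protocol does not establish. The correction is worth making because this is a safety rule tied to a named preclinical signal and the remedy is cheap.

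The conflict between Section 1.4 and Section 5.8 over the liver and QTc criteria is a separate, minor point and adds no weight to this one.

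**What to change.** Reconcile Section 5.8, criterion 10, with Section 6.4.5, footnote b, so that every analyte named in the criterion has the pre-dose values it demands. The mismatch can be closed in the laboratory schedule or in the wording of the criterion; the choice and the clinical content belong to the sponsor's physicians. Chemistry samples are already drawn at Visits 1b and 2 (Table 2; Section 7.1), so a change to the schedule would mean an added test on existing samples, provided that the central laboratory confirms the volume suffices. A change to the criterion would be an edit to the text.

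Separately, align Section 1.4 and Section 5.8 on whether the liver and QTc criteria are mandatory, and on the confirming repeat test that Section 5.8 requires and Section 1.4 does not mention. This too is an edit to the text.
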